##### 3.1.1 Administrative structure of the trial

The trial is sponsored by Boehringer Ingelheim (BI). Boehringer Ingelheim will appoint a Trial Clinical Monitor (TCM), responsible for coordinating the activities required in order to manage the trial in accordance with applicable regulations and internal Standard Operating

Proprietary confidential information.

© 2017 Boehringer Ingelheim International GmbH or one or more of its affiliated companies. All rights reserved.

This document may not - in full or in part - be passed on, reproduced, published or otherwise used without prior written permission.

Procedures (SOPs), directing the clinical trial team in the preparation, conduct, and reporting of the trial, ordering the materials as needed for the trial, ensuring appropriate training and information of local clinical monitors (CMLs), CRAs, and investigators in participating countries.

Data management and statistical evaluation will be done by BI according to BI SOPs. For these activities, a Trial Data Manager and a Trial Statistician will be appointed. Tasks and functions assigned in order to organize, manage, and evaluate the trial will be defined according to BI SOPs. A list of responsible persons will be given in the Clinical Trial Master File (CTMF) document.

[REDACTED] has been selected as service provider to support the following tasks related to the neuropsychological assessments: necessary rater prequalification, rater training (online and at investigator meeting), provision of rater materials and central review of assessments (see [section 8.2](#) for details).

Central laboratory and central ECG service vendors will be used for this trial. The organization of the trial in the participating countries will be done by the respective local BI organization (OPU) or by a Contract Research organization (CRO) with which the responsibilities and tasks have been agreed and a written contract has been filed before initiation of the clinical trial. In each local BI-organisation (OPU) participating in this study, a local clinical monitor (CML) will be appointed responsible for coordinating the activities required in order to manage the trial in accordance with applicable regulations and internal SOPs in the countries covered by the respective BI OPU.

A Coordinating Investigator will be nominated to coordinate investigators at different sites participating in this multi-centre trial. Tasks and responsibilities for the Coordinating Investigator will be defined in a contract filed before initiation of the trial. Documents on participating (Principal) investigators and other important participants, especially their curricula vitae, will be filed in the CTMF.

The Investigator Site File (ISF) will be kept at the sites as far as required by local regulations and BI SOPs. A copy of the ISF documents will be kept as an electronic Clinical Trial Master File.

### **3.2 DISCUSSION OF TRIAL DESIGN, INCLUDING THE CHOICE OF CONTROL GROUP(S)**

All patients who are screening positive will undergo a single blinded placebo run-in phase in order to generally familiarize with the clinical setup of the neuropsychological tests as well as the regular intake of study drug to ensure compliance with study procedures.

A parallel group design is the appropriate design as the inherent within-patient variability and the progressive nature of the disease makes it difficult if not impossible to employ a crossover design.

Treatment with BI 409306 will be compared to treatment with placebo.

**Proprietary confidential information.**

© 2017 Boehringer Ingelheim International GmbH or one or more of its affiliated companies. All rights reserved.

This document may not - in full or in part - be passed on, reproduced, published or otherwise used without prior written permission.

In order to estimate the absolute drug effect on cognition and function, a double-blind comparison against placebo is included in this trial. With this approach we follow the EMA guideline on medical products for the treatment of Alzheimer's disease and other dementias (CPMP/EWP/553/95 Rev. 1, 2008) [[R11-5045](#)].

The current standard treatment of cognitive and functional impairment in AD shows substantial treatment effects during the first three months of treatment. Therefore, a 12-week treatment period is considered to be sufficient to assess the efficacy, tolerability and safety of BI 409306.

The data collected in this double-blind, randomized, placebo-controlled trial are standard in this indication and will provide important information in terms of efficacy and safety on the use of BI 409306 maintenance treatment in patients with mild to moderate AD.

Independent raters for efficiency and AE are strongly recommended because the drug has known side effects which may inadvertently bias the trial team doctors who see the patients for visits. Please refer to section [6.2](#).

### 3.3 SELECTION OF TRIAL POPULATION

Untreated male and female patients, at least 55 years old, with diagnosis of mild Dementia of Alzheimers' Type (DAT) will be randomised. Recruitment will be competitive and participating sites are expected to enter at least **354** patients.

Patients who fail to complete all assessments in terms of primary and secondary endpoints according to the study protocol will not be considered study completers (see [Sections 6.2](#) and [7.3](#) for details). Patients who discontinue following randomisation may not be re-enrolled at a later date. A record is kept of all patients failing to complete all trial visits and their reasons for discontinuation. Re-screening of not yet randomised patients can be allowed in exceptional cases but should be discussed on a case-by-case basis between the study site, Monitor staff and with the TCM.

Permission to randomise more than 15 patients per site must be obtained from the TCM at Boehringer Ingelheim. This will only be allowed after a careful review of the enrolment status.

A log of all patients included into the study (i.e. having given informed consent) will be maintained in the ISF at the investigational site irrespective of whether they have been treated with investigational drug or not.

#### 3.3.1 Main diagnosis for study entry

Patients with the diagnosis of mild Alzheimer's Dementia (according to the Core Clinical Criteria of the recommendations from the National Institute on Aging-Alzheimer's Association workgroups [[R13-4115](#)] on diagnostic guidelines for Alzheimer's Dementia) will be included.

### 3.3.2 Inclusion criteria

Patients are included in this study if they meet all of the following criteria:

1. Diagnosis of mild Alzheimer's Dementia according to the recommendations from the National Institute on Aging-Alzheimer's Association workgroups on diagnostic guidelines for Alzheimer's disease (see [section 3.3.1](#)).
2. Mini-Mental State Examination (MMSE) score of 18-26, an Alzheimer's Disease Assessment Scale – cognitive subscale (ADAS-cog11) score > 12 and a global CDR score of 1 or greater at screening.
3. Patients must have given written informed consent in accordance with GCP and local legislation prior to any study procedures. All patients must be able to give informed consent personally and have capacity for such consent. An informed consent given by a legal representative will not be accepted.
4. Patients must have a reliable study partner (per investigator judgement for instance a family member, partner etc., guardian (must be always the same person)) who is in close contact with the patient, available on call and who is able to contribute to the assessment of the ratings of the functional endpoints including CDR-SB at specific study visits as stated in the [flow chart](#). This person will be able to communicate in the language in which the patient is being assessed and should also serve as a backup contact for the study site. The study partner must sign a separate informed consent form which describes their contributions during the study.
5. Patients must have at least 6 years of formal education and fluency in the test language as verbally confirmed by the patient and documented by the study investigator.
6. Previous use of AD medications (AChEIs, memantine) is allowed up 3 month prior to screening. Patients who are currently taking AChEIs are eligible as long as they have been using a stable dose for at least 3 months prior to screening and no change is foreseen for the duration of the study. This dose must be consistent with the product label in the concerned country. Patients currently taking memantine are excluded. .
7. Male or female patients at least 55 years of age. Patients older than 85 years may be included based on an acceptable general health status, (e.g. concomitant diseases, physical capability to follow the required study procedures [visits etc.]) at discretion of the investigator.

### 3.3.3 Exclusion criteria

Patients must be excluded from this study if they meet any of the following criteria:

1. Dementia secondary to other disorders (for example: neurosyphilis, craniocerebral trauma, small vessel disease) based on clinical data and/or current laboratory findings and/or a pre-existing MRI or CT of the brain. If previous cranial imaging is not available or older than 12 months prior to screening then a CCT or MRI needs to be performed at screening. Please check your local regulations if the use of radiations for a CCT scan is

**Proprietary confidential information.**

© 2017 Boehringer Ingelheim International GmbH or one or more of its affiliated companies. All rights reserved.

This document may not - in full or in part - be passed on, reproduced, published or otherwise used without prior written permission.

allowed in your country. If performing of a CCT is not allowed in the frame of this trial (e.g. Germany, France, United Kingdom), a MRI must be performed.

2. Substantial concomitant cerebrovascular disease (defined by a history of a stroke/intracranial haemorrhage temporally related to the onset of worsening of cognitive impairment) (per investigator judgement).
3. Medical history of cancer (except for basal cell carcinoma) and/or treatment for cancer within the last 5 years.
4. History or diagnosis of the following symptomatic and unstable/uncontrolled conditions (per investigator judgement):
  - a. Uncontrolled cardiovascular illnesses such as chronic congestive heart failure (with or without oedema), tachycardia, arrhythmias, uncontrolled hypertension.
  - b. Significant ischemic heart disease, myocardial infarction within the last two years and/or with residual angina, orthopnea, conduction defects (ECG), or any other clinical significant heart disease classified as NYHA III or IV.
  - c. Significant liver disease (for example cirrhosis, active hepatitis B and C, primary or metastatic liver neoplasm).
  - d. Significant gastrointestinal disorders (for example gastrointestinal bleeding within the last two years, malabsorption syndromes, post-gastrectomy, or active peptic ulcer disease).
  - e. Uncontrolled endocrine disease such as uncontrolled diabetes mellitus or manifest hyperthyroidism.
  - f. Unstable/uncontrolled major depression
  - g. Significant pulmonary disease predisposing to hypoxia.
  - h. Immunological disorder such as per investigator judgement clinically significant allergies, Lupus erythematoses, or scleroderma.
  - i. Uncontrolled/Unstable haematological disease (regardless of cause) such as refractory anaemia or refractory myelosuppression.
  - j. Systemic or multiple organ dysfunctions which, in the opinion of the investigator, would impact on the primary and secondary endpoints of the trial such as clinically relevant dehydration
5. Severe renal impairment defined as a GFR < 30 mL/min/1.73 m^2 in the screening central lab report.
6. Neurological disease (other than DAT such as: Lewy body dementia – primary diagnosis, Huntington's disease, Parkinson's Disease, encephalitis, epilepsy, vascular or multi-infarct dementia, stroke, congenital mental deficiency, multiple sclerosis) and psychiatric disorders such as schizophrenia, or mental retardation.
7. Any suicidal behaviour in the past 2 years (i.e. actual attempt, interrupted attempt, aborted attempt, or preparatory acts or behaviour).

**Proprietary confidential information.**

© 2017 Boehringer Ingelheim International GmbH or one or more of its affiliated companies. All rights reserved.

This document may not - in full or in part - be passed on, reproduced, published or otherwise used without prior written permission.

8. Any suicidal ideation of type 4 or 5 in the C-SSRS in the past 3 months (i.e. active suicidal thought with intent but without specific plan, or active suicidal thought with plan and intent).
9. Previous participation in investigational drug studies of mild cognitive impairment/DAT within three months prior to screening. Having received active treatment in any other study targeting disease modification of AD like A $\beta$  immunization and tau therapies. Previous participation in studies with non-prescription medications, vitamins or other nutritional formulations is allowed.
10. Significant history of drug dependence or abuse (including alcohol, as defined in Diagnostic and Statistical Manual of Mental Disorders [DSM-V] or in the opinion of the investigator) within the last two years, or a positive urine drug screen for cocaine, heroin, or marijuana.
11. Known history of HIV infection.
12. Bodyweight < 50 kg.
13. Planned elective surgery requiring general anaesthesia, or hospitalisation for more than 1 day (requiring an overnight stay) during the study period.
14. Pre-menopausal women (last menstruation  $\leq$  1 year prior to informed consent) who:
  - are nursing or pregnant or
  - are of child-bearing potential and are not practicing an acceptable method of birth control, or do not plan to continue using this method throughout the trial until 28 days after the last treatment administration, and do not agree to submit to periodic pregnancy testing during participation in the trial. Acceptable methods of birth control include tubal ligation, vasectomized partner (and this has to be the patient's sole partner), transdermal patch, intra uterine devices/systems (IUDs/IUSs), combined estrogen-progestin oral contraceptives as well as implantable or injectable hormonal contraceptives unless they are a moderate to strong CYP1A2 inhibitor – see [section 4.2.2.1](#). Complete sexual abstinence (if acceptable by local health authorities) is allowed when this is in line with the preferred and usual lifestyle of the subject. Periodic abstinence (e.g., calendar, ovulation, symptom-thermal, post-ovulation methods) and withdrawal are not acceptable methods of contraception. Double barrier methods are permissible (if acceptable by local health authorities, note that this is not an acceptable method in EU countries).
15. For male patients: Men who are able to father a child, unwilling to be abstinent or to use an adequate form of effective contraception for the duration of study participation and for at least 28 days after treatment has ended.
16. Use of any investigational drug or procedure within 3 months or 6 half-lives (whichever is longer) prior to randomisation.
17. The following drugs are prohibited for 3 months prior to randomisation and for the duration of the trial:
  - a. tricyclic antidepressants,
  - b. antidepressants that are monoamine oxidase inhibitors,

Proprietary confidential information.

© 2017 Boehringer Ingelheim International GmbH or one or more of its affiliated companies. All rights reserved.

This document may not - in full or in part - be passed on, reproduced, published or otherwise used without prior written permission.

- c. neuroleptics with moderate or greater anticholinergic potency (eg, chlorpromazine, fluphenazine, loxapine, perphenazine, thioridazine),
- d. anticholinergic medications,

The following drugs may be given as needed if the total daily dose was stable 8 weeks prior to randomisation and is expected to be for the duration of the trial:

- a. neuroleptics listed in section [4.2.2.](#),
- b. benzodiazepines and sedatives listed [4.2.2.](#)

18. Indication of liver disease, defined by serum levels of either ALT (SGPT), AST (SGOT), or alkaline phosphatase above 3 x upper limit of normal (ULN) as determined during screening
19. Any other clinical condition that, in the opinion of the investigator, would jeopardize patient safety while participating in this clinical trial
20. Incompliance with study drug intake defined as a compliance <75% during the run-in phase
21. Clinically significant uncompensated hearing loss in the judgement of the investigator. Use of hearing aids is allowed.
22. Known hypersensitivity to the drug product excipients (gelatin, povidone K25, lactose monohydrate, microcrystalline cellulose, pregelatinized starch, hydroxypropylcellulose, croscarmellose sodium, magnesium stearate, hypromellose, propylene glycol, titanium dioxide, talc and iron oxide yellow).

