## FLOW CHART

Trial Period	Screening	Placebo Run-in Period	Treatment Period							Follow-up
			3 Baseline	4a 	4b 	4c 	5	6	EOT/ED 	
Visit	1	2		1	2	3	4	8	12	16
Studyweeks	-3	-2		1	2	3	4	8	12	16
Study-Day (or duration during screening/ run-in)	Duration 1-7 days	Duration at least 14 and at most 21 days after screening period	1	8	15	22	29	57	85	EOT +28
Visit window (in days)				±1	±1	±1	±3	±3	+3	±3
Patient information & informed consent signed ████████████████████	X									
Register Patient in IRT	X									
Randomisation (via IRT)			X							
Demographics	X									
Medical history / baseline conditions	X									
In-/exclusion criteria	X	X	X							
Imaging of the Brain 	X									
Concomitant medications	X	X	X	X	X	X	X	X	X	X
Height (screening only)/weight	X								X	X
Vital signs	X		X	X	X 	X 	X	X	X	X
Post Dose Heart Rate Procedure 			X							
Physical examination	X								X	
Neurological examination	X								X	
Resting ECG (digital)	X		X	X	X 	X 	X	X	X	X
Adverse events	X	X	X	X	X 	X 	X	X	X	X
Dispense trial medication 		X	X				X	X		
Collect study drug			X				X	X	X	
Medication Compliance Check			X				X	X	X	
Laboratory tests: Chemistry, haematology, urinalysis	X		X				X	X	X	X
Blood Glucose (Onsite) 	X		X				X		X	
████████████████████			█					█		
████████████████████			█						█	
Urine drug screen	X								X	
Urine pregnancy test 	X		X				X	X	X	
Vitamin B12 and folate	X								X	
RPR (FTA, if RPR positive)	X									
Prospective Suicidality Monitoring										
C-SSRS	X 	X 	X 	X 	X 	X 	X 	X 	X 	X 

Proprietary confidential information.

© 2017 Boehringer Ingelheim International GmbH or one or more of its affiliated companies. All rights reserved.

This document may not - in full or in part - be passed on, reproduced, published or otherwise used without prior written permission.

Trial Period	Screening	Placebo Run-in Period	Treatment Period							Follow-up
			3 Baseline	4a 	4b 	4c 	5	6	EOT/ED 	
Visit	1	2								FU
Studyweeks	-3	-2		1	2	3	4	8	12	16

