#### Human urine chorionic gonadotropin (HCG)

---

- Pregnancy testing (HCG, urine) will be performed in female patients of child bearing potential only according to the time points indicated in the [Flow Chart](#) or if required by local regulations more frequently or in plasma instead of urine

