### 6.2.1 Screening and run-in period(s)

#### Visit 1 (screening)

- Patients must sign Informed Consent ( [REDACTED] ) before any study related procedures are performed.
- The patient should be recorded on the enrolment log and be registered in the IRT as a screened patient.
- Study procedures have to be completed according to the [Flow Chart](#).
- Demographics include age, educational level, current or past professional experience
- ECG and vital sign measurement will be performed.
- For diabetic patients with antidiabetic therapy: exclusion of hypoglycemia for the period of the neuropsychological assessment (documented plasma glucose concentration  $\geq 90$  mg/dl (5mmol/l) at the beginning and directly after the assessment). If glucose is too low patients need to eat a snack and then be retested to confirm that the blood sugar value is above 90 mg/dl before the tests are started
- Blood pressure must always be measured before taking any blood sample.
- A complete physical examination and neurological examination.
- Laboratory samples will be collected as described in the flow chart.
- Assessment for MRI (if no pre-existing MRI or CT of the brain is already available (please refer to [inclusion criteria](#) for details)) must be scheduled in order that results are available prior to Visit 2
- Administer the following neuropsychological assessments in the following order:

Proprietary confidential information.

© 2017 Boehringer Ingelheim International GmbH or one or more of its affiliated companies. All rights reserved.

This document may not - in full or in part - be passed on, reproduced, published or otherwise used without prior written permission.

- MMSE
- CDR
- ADAS-cog11
- Administration of C-SSRS (baseline/screening scale)
- Once Visit 1 procedures are complete and laboratory results are received, inclusion/exclusion criteria must be reviewed again. If the patient is still eligible according to inclusion/exclusion criteria, the patient should be contacted to schedule next visit.
- If a patient does not meet inclusion/exclusion criteria the patient must be recorded in CRFs as a screen failure. Patient must be registered as screen failure in IRT.

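### Exclusion 14 ties refusal of pregnancy testing to the contraception conditions with *and*, so read literally it admits women it is evidently meant to exclude

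*Protocol*

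**What the plan says.** Protocol Section 3.3.3 opens with "Patients must be excluded from this study if they meet any of the following criteria", so the logic inside each criterion decides who may enter.

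Exclusion 14 concerns pre-menopausal women, defined by a last menstruation no more than one year before consent. It has two bullets joined by *or*. The first covers women who "are nursing or pregnant or". The second covers women of child-bearing potential and has three parts:

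- not using an acceptable contraceptive method;
- *or* not planning to keep using it for the required period;
- *and* not agreeing to testing.

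The join between the last two parts reads "until 28 days after the last treatment administration, and do not agree to submit to periodic pregnancy testing".

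The same bullet then sets out which methods count. It states, for example: "Periodic abstinence (e.g., calendar, ovulation, symptom-thermal, post-ovulation methods) and withdrawal are not acceptable methods of contraception".

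Exclusion 15 gives the rule for men: "Men who are able to father a child, unwilling to be abstinent or to use an adequate form of effective contraception", for the study and at least 28 days after treatment.

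Testing itself is a trial procedure. Section 5.2.3 says "Pregnancy testing (HCG, urine) will be performed in female patients of child bearing potential only according to the time points indicated in the" flow chart. The flow chart row "Urine pregnancy test" has marks at Visits 1, 3, 5, 6 and EOT, and none at follow-up. A footnote allows more frequent testing where local regulations require it.

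**The concern.** The second bullet has the form *A, or B, and C*. A patient is excluded only if the whole expression is true, so joining C with *and* narrows the exclusion. Agreeing to be tested can then make a woman eligible even though her contraception plans fall short of the protocol's own standard.

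The rest of the text points to three conditions that each exclude on their own:

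- The detailed list of acceptable and unacceptable methods has little purpose if a non-user can enter by accepting a test.
- Exclusion 15 makes contraception a stand-alone requirement for men.
- Section 5.2.3 makes testing part of the safety laboratory programme, not an alternative to contraception.
- Amendment 4 revised exclusion 14 to remove hormonal contraceptives that are moderate to strong CYP1A2 inhibitors, so the sponsor treats it as a live safety rule.

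At stake is protection against pregnancy exposure to an experimental drug. The statistical analysis is not involved.

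**Working it through.** The plan gives no figure to reproduce. The check is a truth table plus a reading of the test schedule.

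**Definitions**, for a woman of child-bearing potential (exclusion 14, second bullet):

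- A = not using an acceptable method
- B = uses one now but does not plan to continue it until 28 days after the last dose
- C = does not agree to periodic pregnancy testing

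**Groupings**

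- G1: (A or B) and C, which the commas suggest
- G2: A or (B and C)
- Intended: A or B or C

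A third grouping, (child-bearing potential and A) or (B and C), gives the same result as G2 for these women.

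**Patient types**: 3 contraception states × 2 attitudes to testing = 6.

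| Contraception | Testing | G1 excludes | G2 excludes | Intended excludes |
|---|---|---|---|---|
| Non-user | accepts | no | yes | yes |
| Non-user | refuses | yes | yes | yes |
| User, plans to stop | accepts | **no** | **no** | yes |
| User, plans to stop | refuses | yes | yes | yes |
| User, will continue | accepts | no | no | no |
| User, will continue | refuses | **no** | **no** | yes |
| **Total excluded** | | **2** | **3** | **5** |

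Types missed: 5 − 2 = 3 under G1 and 5 − 3 = 2 under G2. The two in bold are missed under both. G1 also misses the non-user who accepts testing.

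**Does anything else exclude them at entry?**

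- *Other criteria.* No other eligibility criterion requires contraception in women. Exclusion 19 covers a clinical condition that endangers safety; a plan to stop contraception is not obviously one.
- *The refuser.* Tests are due at Visits 1 and 3, before the first randomised dose. Section 6.2.1 adds "Once Visit 1 procedures are complete and laboratory results are received, inclusion/exclusion criteria must be reviewed again". A woman who refuses is therefore partly caught by procedure.
- *The planned stop.* Agreeing to testing does not replace B. There are 5 scheduled tests up to EOT and 0 at follow-up, so the 28 days after the last dose rest on contraception alone unless local rules add a test.
- *SAP Table 6.2:1.* Exclusion 14 is not among the listed eligibility violations, although the table may be supplemented. Item E1 flags a missing negative pregnancy test and does not address contraception plans.

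**The case against.** The strongest reply is that *and* need not be a logical operator. In a list of women to be excluded it can be additive: women who do A or B, and also women who do C. Each condition would then exclude on its own, and most investigators would probably apply it that way. That is a fair prediction of practice. But this reading needs a repeated subject that the sentence lacks, and an entry rule should not depend on the reader supplying it.

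Second, there are safeguards. Testing is mandatory on schedule, Section 3.3.4.1 allows discontinuation for non-compliance and requires withdrawal on pregnancy, drug exposure during pregnancy must be reported within 24 hours, and SAP item E1 flags a missing negative test. This stands for the refuser, whose case has little practical force. For the woman who plans to stop, these measures only detect a pregnancy after it occurs; they do not keep her out.

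Third, the untested 28 days may carry little risk. Section 5.2.2.2 sets the residual effect period at 7 days, and Section 4.1.3 reports CSF levels below quantification 8 to 14 hours after dosing, roughly in parallel with plasma. This reduces the likely harm but does not displace the 28-day contraception period that the protocol itself sets.

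Fourth, the counts out of six are cells of a truth table, not patients. That is correct: they show how far the wording departs from the intent and say nothing about how often it would matter.

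**Conclusion.** The concern holds, as a minor one. As written, exclusion 14 fails to exclude 2 or 3 of the 5 patient types it evidently targets. A user who plans to stop but accepts testing, and a continuing user who refuses testing, are missed under every logical grouping. The gap that matters is the planned stop, because nothing in the available documents screens for it. Consent pages and the site file were not available, so a contraception duty stated there cannot be ruled out.

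The conclusion assumes that *and* is read as a logical connector and that the three conditions were each meant to exclude alone; the surrounding text supports the second assumption.

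The practical impact is very small. The documents give no count of affected women. With a minimum age of 55 and menstruation within the past year, it is probably near zero of the 354 planned patients; that is a judgement, not a documented figure. No efficacy result, alpha or power changes.

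**What to change.** In exclusion 14, second bullet, replace the *and* before the testing condition with *or*, and set out three separate bullets for women of child-bearing potential:

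- not practising an acceptable method;
- not planning to continue it until 28 days after the last dose;
- not agreeing to periodic pregnancy testing.

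Only a woman who uses an acceptable method, will continue it and accepts testing then remains eligible.

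The cost is one word and a layout change at the next amendment, with practically no effect on recruitment.
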